7.2 Data Collection Technologies

7.2.1 The PRO-Diary

The PRO-Diary is a wrist-worn accelerometer enhanced with a user interface that allows for input of real-time self-reported data. The PRO-Diary will be used in this study to provide optimally sensitive assays of fatigue intensity, fatigue impact, physical activity, and fatigability (calculated using fatigue severity and activity measures). Ratings at wake and bedtime will be initiated by the participant upon waking (not necessarily when they get out of bed) and at bedtime ("lights out" or the time they intend to go to sleep, not necessarily the time they get into bed). An audible alarm will alert participants to use the touch screen to log symptom ratings at 2 times between 11am and 7pm. The PRO-Diary collects physical activity data as 'activity counts' in 15 second epochs during the home monitoring period and stores time-stamped self-report data until the watch is returned to the lab, for data download, cleaning and analysis. The PRO-Diary also generates accelerometer-derived sleep variables, based on physical activity during sleep. These variables include, sleep duration, wake after sleep onset, sleep latency, and sleep efficiency.

7.2.2 REDCap

This study will use REDCap, a secure, password protected, and HIPAA compliant web-based data platform hosted by the Michigan Institute for Clinical and Health Research (MICHR) at the UM for data capture and storage. This protected database will be accessed and maintained by study personnel only. This system features both a local and remote web-based interface, secure data transfer, and an Oracle database. Data security, patient privacy, and HIPAA requirements are a premium consideration for clinical trials research using REDCap. A complete time-stamped audit of all REDCap activity (including which and when study personnel access data) is maintained, adding to the security and fidelity of the data. Study personnel can enter data into the database through administrative access to add to the self-report data provided by participants. For self-report data collection, participants will access individualized study urls to securely enter data either during clinic visits or at a time of their choosing on an internet-connected device of their choosing (for home-based assessments).

Participant email addresses will be used to send the follow-up survey links. Participant emails will be stored in REDCap. The University of Washington study staff will be able to view only email addresses of University of Washington participants, but as the data coordinating center, the University of Michigan study staff will have access to email address for all study participants, including those from University of Washington.

7.2.3 M+Box

Transfer (from UW to UM) of accelerometer/EMA data from the PRO-Diary will be achieved via M+Box, which is Michigan's implementation of the Box.com cloud storage and collaboration service. It is capable of handling PHI and other sensitive data (e.g., research data). We have used M+Box extensively in previous studies to transfer PRO-Diary data to the lead site for data cleaning and analysis. After it is cleaned and scored, the PRO-Diary data will be later merged with the REDCap data prior to analysis.

7.2.4 SignNow

This study will use SignNow to request and obtain digital signatures on informed consent document from participants who conduct their baseline visit virtually. SignNow software is an E-Signature service available for use by U-M staff, faculty, researchers, and students associated with all University of Michigan campuses (i.e., Ann Arbor, Dearborn, Flint and Michigan Medicine). SignNow is HIPAA and FDA 21 CFR Part 11 compliant for patient signatures.

7.3 General Medical History

General medical history will be assessed at baseline and in all follow-up visits. Subjects will be queried about any chronic or ongoing health conditions pertinent to MS, fatigue, or potential Modafinil side effects that require treatment (which will be recorded in the CRF). Subjects will also be asked to provide their list of medications and allergies.

7.4 Concomitant Medication Use

Concomitant medications will be assessed at each visit and/or phone contact and recorded in the CRF.

7.5 Adverse Event Assessments

Adverse events that are NOT related to the normal course or chronic symptoms of MS (such as relapses, MRI progression, somatic pain, weakness, numbness, visual disturbances, bladder/bowel symptoms) or events that are expected to occur in the course of daily life or use of disease modifying therapy (injuries, infections, disease modifying therapy infusion reactions, disease modifying therapy injection site reactions, disease modifying therapy-induced lymphopenia) **will be assessed/collected at each visit, scheduled phone call, or unscheduled phone call.**

Participants will be queried about any symptoms they have been experiencing while on the study, with directed questions toward adverse outcomes previously reported with the study treatments (including headache, nausea, nervousness, rhinitis, diarrhea, anxiety, insomnia, dizziness, dyspepsia, worsening depressive symptoms, psychosis, increased suicidality) or suspected allergic reactions: rash, hives, mouth sores, blisters, swelling of your face, eyes, lips, tongue, or throat, trouble swallowing or breathing, fever, shortness of breath, swelling of the legs, yellowing of the skin or whites of the eyes, or dark urine.

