Modafinil: Use of modafinil involves a minor increase over minimal risk. Modafinil is generally considered to be safe and well tolerated. The most common adverse reactions (5%) associated with modafinil which occurred more frequently than placebo-treated patients in previous clinical trials were headache, nausea, nervousness, rhinitis, diarrhea, back pain, anxiety, insomnia, dizziness, and dyspepsia. It is recommended that caution be used in patients with a history of psychosis, depression, or mania, to avoid exacerbation of these conditions. Serious rash requiring hospitalization and discontinuation of treatment has rarely been reported. Life-threatening skin conditions such as Steven-Johnson Syndrome or Toxic Epidermal Necrosis Syndrome, angioedema, anaphylaxis, hypersensitivity reactions involving multiple organs, new or increased psychiatric symptoms (including worsening depression, mania, depression, suicidality), or increased blood pressure are possible. Dose reduction is recommended in patients with severe hepatic impairment. Modafinil use may decrease the effectiveness of hormonal contraception, use of alternative or concomitant methods of contraception while taking modafinil and for one month after discontinuation of modafinil treatment is recommended. Elimination of drugs that are substrates for CYP2C19 (e.g., phenytoin, diazepam, propranolol, omeprazole, and clomipramine) may be prolonged by modafinil via inhibition of metabolic enzymes, with resultant higher systemic exposure.

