All potential risks of modafinil will be outlined in the informed consent document and discussed with the patient prior to enrollment. Patients will also be advised that there may be unforeseen risks not outlined in the ICF. Based on the package insert, eligibility criteria will exclude pregnant women, and a urine pregnancy test will be required prior to study enrollment. Women of childbearing age will be advised of the risk of decreased effectiveness of hormonal contraception with modafinil use and be advised to use a form of birth control that does not involve hormonal contraception (spermicide or condoms) during the study and for one month after discontinuation of modafinil treatment. Participants with a history of hepatic impairment, participants over age 65, and participants who use warfarin, phenytoin, MAOIs and cyclosporine will be given dose limitations that will not exceed half of the maximal daily dose for healthy patients (50-100 mg once-twice daily as tolerated). Patients will be advised to monitor for common side effects of modafinil including headache, nausea, nervousness, rhinitis, diarrhea, back pain, anxiety, insomnia, dizziness, and dyspepsia while on modafinil, and if these symptoms occur or worsen, to alert the study team, during which time dose reduction or discontinuation will be discussed. Participants who experience worsening depressive symptoms, psychosis, increased suicidality, or suspected allergic reactions (rash, hives, mouth sores, blisters, swelling of the face, eyes, lips, tongue, or throat, trouble swallowing or breathing, fever, shortness of breath, swelling of the legs, yellowing of the skin or whites of the eyes, or dark urine) will be instructed to stop treatment immediately and contact the study team. Participants are also advised not to consume alcohol per the drug label. Participants should be instructed to call study team when new drugs are added or removed from their drug regimens so that drug interactions can be assessed. Participants may choose to discontinue their treatment at any time if they experience any untoward effects that they believe are related to modafinil, but will be encouraged to remain in the study until completion for monitoring. Adverse events and severe adverse events will be assessed/reported regularly and on an as-needed basis in accordance with the protocol, GCP, and IRB standards (see sections 7.5 and 8). Action involving possible PI discontinuation of study drug will be determined promptly in accordance with the protocol, GCP and IRB guidelines, as well as the medical monitor (see section 10 and 13).

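### Section 7.5 leaves back pain out of the directed adverse-event questions and makes attribution to MS a condition of recording a non-serious event, which can distort the Aim 3 comparison in a direction the documents do not settle

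*Combined protocol and SAP*

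**What the plan says.** Section 7.5 (Adverse Event Assessments) defines what is collected by what is left out: "Adverse events that are NOT related to the normal course or chronic symptoms of MS (such as relapses, MRI progression, somatic pain", followed by further MS symptoms including bladder and bowel complaints. The same sentence goes on to "or events that are expected to occur in the course of daily life or use of disease modifying therapy (injuries, infections" and reactions to disease modifying therapy. Events that pass are collected at visits and at scheduled and unscheduled calls.

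Section 7.5 then provides an open question about any symptoms, with directed questions on outcomes already reported with the study treatments: "including headache, nausea, nervousness, rhinitis, diarrhea, anxiety, insomnia, dizziness, dyspepsia, worsening depressive symptoms, psychosis, increased suicidality", plus signs of allergy.

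Section 1.3 (Safety, Modafinil) introduces its list as "The most common adverse reactions (5%) associated with modafinil" and names "headache, nausea, nervousness, rhinitis, diarrhea, back pain, anxiety, insomnia, dizziness, and dyspepsia". The advice to participants in 1.3 repeats back pain: "Patients will be advised to monitor for common side effects of modafinil including headache, nausea, nervousness, rhinitis, diarrhea, back pain". The footnote to the stopping rules in section 13 gives the same ten.

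Section 8.1 has a five-grade relatedness scale. Section 8 sends the medical monitor the adverse events collected under 7.5, and all SAEs whatever their relatedness or expectedness. Section 9.2 (Aim 3) describes incidence, type, severity and relatedness by arm and compares adverse-event frequency between arms.

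**The concern.** Two features of 7.5 act on the same event. Back pain is recognised three times as a common modafinil reaction, yet it is the only one of the ten that staff are not directed to ask about. It also resembles one of the MS symptoms that 7.5 gives as grounds for not collecting an event. A participant who does mention it may have it treated as MS pain, and then nothing is recorded.

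The judgement of cause is therefore made before the record exists, although 8.1 already provides a place to make it afterwards. This matters because Aim 3 compares arms that differ in exposure to the drug, and the people assessing safety know the arm. An ambiguous pain could be kept in one arm and set aside in another, and the adverse-event dataset would not show it.

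**Working it through.** The plan states no figure on this point, so the check is a comparison of texts followed by an illustrative count.

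**Step 1: the two lists.**
- Section 1.3 names ten common reactions, and section 13 names the same ten.
- The directed questions in 7.5 name twelve items before the allergy signs.
- Nine of the ten reactions in 1.3 appear in 7.5, in the same order. The one missing is back pain (10 − 9 = 1).
- The 7.5 list adds worsening depressive symptoms, psychosis and increased suicidality (9 + 3 = 12). No reason is given for dropping back pain.

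**Step 2: the path of a non-serious back pain.**
- Prompted: no.
- Volunteered: possible, through the open question in 7.5 or the self-monitoring advice in 1.3.
- If volunteered and judged an MS symptom: not collected under 7.5, so it gets no 8.1 grade, does not reach the medical monitor and does not enter the Aim 3 analysis.
- If volunteered and not so judged: collected and graded.

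**Step 3: who handles it.** Section 6.6 has coordinators carry out safety assessments under the supervision of the study PIs. Section 5.2 says that both are unblinded. No section says who applies the MS or daily-life filter.

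**Step 4: other sources of difference between arms.** The footnote to the schedule in 6.9 gives Groups 2 and 3 two extra adverse-event reviews, at 2–4 and 7–10 days after starting modafinil. Group 1 has no counterpart. This raises capture in the modafinil arms, while the filter may lower it.

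**Step 5: an illustrative count.**
- Modafinil participants: 2 × 100 = 200, from about 100 per arm (5.1 and 6.3, with the combination arm inferred from 1:1:1 and 300 completers), or 330 × 2/3 = 220, from planned enrollment in 4.0.
- Incidence *r*: assumed. Section 1.3 prints 5% once for the whole list and gives no rate for back pain.
- Share missed *m*: unknown, so 0 to 1.
- Expected cases = n × r: 200 × 0.05 = 10 and 220 × 0.05 = 11. With r = 0.10 (also assumed), 20 and 22.
- Cases missed = n × r × m: 0 to 11 at r = 0.05, and 0 to 22 at r = 0.10.

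The range runs from zero to everything, so the documents do not fix the size of the loss. The count also includes background back pain: 1.3 says only that these reactions exceeded placebo, and it is the excess over CBT that would matter for Aim 3.

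**The case against.** The best defense is that the plan has several routes to this event. The open question covers any symptom, and the directed list is introduced as examples. Section 1.3 tells participants to watch for back pain by name and to contact the team. The section 13 footnote names it among the side effects that lead to stopping and possible re-challenge. The filter is a disclosed choice, explained at the start of section 8 by the many symptoms of MS and the use of standard treatments. SAEs reach the medical monitor regardless of relatedness.

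All of this stands, and it rules out several stronger readings that a reader might draw:
- **Back pain is never asked about, so about 11 of 220 cases are lost.** This assumes that nothing is volunteered and that 5% is the rate for back pain itself. The text supports neither.
- **Somatic pain is excluded outright.** It is excluded when related to MS. New pain after starting modafinil is not excluded by the wording; the risk is misattribution.
- **Rhinitis and diarrhea are dropped as infections.** Both are in the directed questions, and nothing in 7.5 says they are set aside.
- **Unblinded coordinators decide the attribution.** They conduct the assessments, but the decision is assigned to no one.
- **Harm is understated in two arms.** The extra reviews and the self-monitoring advice push the other way, so the net direction is unknown.
- **The loss is wholly irrecoverable.** Medical history (7.3), concomitant medication (7.4) and the Brief Pain Inventory hold some evidence on pain by arm. They are not graded adverse events, and 6.6 says the surveys are not collected for safety.

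What the defense does not answer is that one listed reaction is unprompted and that a non-serious event attributed to MS leaves no adverse-event record.

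**Conclusion.** The concern holds in a limited form. The directed list in 7.5 is inconsistent with sections 1.3 and 13 by one item, and 7.5 places attribution to MS ahead of recording for non-serious events. Because assessors and supervisors are unblinded, the Aim 3 comparison can be distorted. Neither the direction nor the size can be derived from the documents; the figure of 10 to 11 expected cases rests on an assumed 5% incidence, with capture anywhere from none to all. The primary endpoint is not affected.

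A secondary point is the wording of the collection sentence. Read literally, "events that are expected to occur in the course of daily life" could be among the events collected; the rationale opening section 8 favors exclusion. Two sites could apply it differently.

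**What to change.** In section 7.5:
- Add back pain to the directed questions, so that the list agrees with sections 1.3 and 13.
- State that any reaction listed in 1.3 is recorded in all three arms whatever its presumed cause, and that attribution to MS or daily life is made afterwards on the 8.1 scale.
- Reword the collection sentence so that it is clear whether daily-life events are collected, and say who makes the attribution.

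The cost is one checklist item, some rewording, and more background events recorded in every arm. Those can be separated at analysis by the relatedness grade, which is not possible for events that were never recorded.

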6.9 SCHEDULE OF ACTIVITIES

Study Activity	Baseline (week -1 to -2)	Weeks 1-7**	Week 8	Weeks 9-11	Week 12	Weeks 13-23	Week 24
Demographics	X						
Medical/Surgical History	X		X		X		X
Interview with a Neurologist for assessment of eligibility	X						
Krupp's Fatigue Severity Scale (FSS)	X						
Patient Health Questionnaire-3	X						
Medication review	X		X		X		X
Baseline urine Pregnancy test if applicable	X						
AE/SAE review (all participants)*	X		X		X		X
Randomization	X						
Modafinil dispensing (for Groups 2 and 3)	X		X				
Study Intervention Administration		X	X	X	X		
Treatment adherence			X		X		
Treatment Utilization Patterns (post-intervention)							X
Excess modafinil destruction (if applicable)					X		
Computer-based self-report measures							
Modified Fatigue Impact Scale (MFIS)	X		X		X		X
EDSS self-report	X						
STOP-BANG questionnaire	X						
RLS Index	X						

Epworth Sleepiness Scale	X		X		X		X
Insomnia Severity Index	X						
Sleep Hygiene Index	X		X		X		X
Patient Health Questionnaire-8	X		X		X		X
Generalized Anxiety Disorder-7	X		X		X		X
Brief Pain Inventory	X		X		X		X
Exercise (Godin)	X		X		X		X
PROMIS Self-Efficacy Scale	X		X		X		X
PROMIS Cognitive Function	X		X		X		X
MSQOL54- Quality of Life Subscale	X		X		X		X
NeuroQoL Ability to Participate in Social Roles & Activities	X		X		X		X
Post-Treatment Questionnaire					X		X
Patient Global Impression of Change					X		X
7-day home monitoring (PRO-Diary) measures							
Physical Fatigue Severity (4x/day)	X				X		
Mental Fatigue Severity (4x/day)	X				X		
Physical Fatigue Impact (4x/day)	X				X		
Mental Fatigue Impact (4x/day)	X				X		
Wake up time (1x/day)	X				X		
Bed time (1x/day)	X				X		
Sleep refreshed (1x/day)	X				X		
Rest breaks (1x/day)	X				X		
Cognitive clarity (1x/day)	X				X		
Cognitive speed (1x/day)	X				X		

Pain Severity (1x/day)	X				X		
Daytime physical activity (continuous)	X				X		

* For Modafinil-treated participants in Group 2 and 3, AE/SAE review will be additionally assessed at the following time intervals:

- 2-4 days after starting Modafinil
- 7-10 days after starting Modafinil

**Activities marked Week 1-7 begin after the baseline assessments, which include a 7-day home monitoring period.

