Aim 3: Compare adverse events, side effects, treatment adherence, and patient dropout rates among the three treatment arms and patient subgroups of interest. Descriptive statistics will be used to analyze patterns of adverse events including side effects (incidence, type, severity, and relatedness) and treatment adherence between treatment groups (modafinil vs. CBT vs. combination therapy) throughout the 12-week intervention interval. Adverse event frequency between treatment groups and among subgroups of interest will be evaluated using ANOVA. Multiple linear regression models adjusted for age, gender, EDSS score, baseline fatigue level, baseline activity level, presence of sleep disorder (yes/no), and depression severity (PHQ-8 Score) will be used to determine association between treatment group and treatment adherence (percent usage of prescribed therapy). We also will assess whether degree of treatment effects measured in Aim 1 are related to treatment adherence (e.g. “dose response”).

9.3 Analysis of Exploratory Aims:

Additional analyses modeled as in 9.2 above will also evaluate treatment effect on the difference between 8 week and baseline MFIS scores, to assess whether treatment effects are detectable prior to the 12-week assessment period.

Additional analyses modeled as in 9.2 above will also evaluate treatment effect on the difference between 24 week and baseline MFIS scores, to assess whether treatment effects are detectable following the 12-week assessment period.

Descriptive statistics will be used to summarize clinical treatment utilization patterns between 12-24 weeks, following the 12-week intervention interval.

Analyses modeled as in 9.2 will also be used to evaluate treatment effects on other outcomes at 12 and 24 weeks. We will examine differential treatment effects on changes in the following

factors (assessed via survey): ability to participate in social roles and activities, pain interference, quality of life, and self-efficacy for managing MS symptoms. We will also examine differential treatment effects on changes from baseline to 12 and 24 weeks in the following outcomes that were assessed via survey and/or EMA: pain intensity, perceived cognitive functioning, and pacing behaviors. Treatment group differences in scores on the PGIC measure at 12 and 24 weeks will be examined in models similar to the approach described in 9.2.

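### Aim 3 has no rule for symptoms already present at baseline, so background symptoms can blur or distort the arm comparison of adverse events, and the between-subgroup comparison does not measure differential harm

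*Combined protocol and SAP*

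**What the plan says.** Section 7.5 sets the elicitation question: "Participants will be queried about any symptoms they have been experiencing while on the study, with directed questions toward adverse outcomes previously reported". The directed list includes headache, nausea, nervousness, anxiety, insomnia and dizziness. Only two of its items are worded as a change: "dyspepsia, worsening depressive symptoms, psychosis, increased suicidality" is the part of the list where depression and suicidality carry that wording. The same section limits collection to "Adverse events that are NOT related to the normal course or chronic symptoms of MS" and also sets aside events expected in daily life or from disease modifying therapy.

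Section 7.3 adds a history: "Subjects will be queried about any chronic or ongoing health conditions pertinent to MS, fatigue, or potential Modafinil side effects that require treatment". Section 6.9 schedules an AE/SAE review for everyone at baseline and at Weeks 8, 12 and 24. Its footnote adds: "For Modafinil-treated participants in Group 2 and 3, AE/SAE review will be additionally assessed at the following time intervals", namely 2-4 and 7-10 days after starting the drug.

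Section 9.2 (Aim 3) describes adverse events by "incidence, type, severity, and relatedness" over the 12-week intervention, and then states: "Adverse event frequency between treatment groups and among subgroups of interest will be evaluated using ANOVA". The subgroups named for Aim 2 in the same section are clinically significant depression, progressive subtype and higher EDSS, and confirmed or suspected sleep disorder. Interaction terms are specified there for fatigue outcomes; none is specified for adverse events.

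**The concern.** The harms comparison is one of the trial's three aims. A trial that enrols fatigued people and measures their anxiety, insomnia and depression at baseline should expect some of them to have directed-list symptoms before treatment starts. Without a rule tying later reports to the baseline review, a long-standing symptom can enter the count as an event.

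Two consequences follow. In the arm comparison, reports unconnected with treatment are mixed with those that may be caused by it, and the arms are not questioned equally often. In the subgroup comparison, a group partly defined by having insomnia will tend to report insomnia whatever the treatment does. Even without that overlap, a difference in event frequency between subgroups is a statement about the patients, not about whether modafinil, CBT or the combination is more harmful in one group than in another. A reader of the results could take it for the latter.

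**Working it through.** **Stated figure.** The plan gives no adverse event rate or power for the harms comparison, so there is nothing to reproduce. All event rates below are assumptions.

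**Step 1: does any existing provision act as a counting rule?**
- The baseline AE/SAE review (6.9) is scheduled, but neither 7.5 nor 9.2 refers to it as a reference.
- The exclusion of chronic MS symptoms (7.5) gives examples such as pain, weakness, numbness, visual and bladder or bowel symptoms. Anxiety, insomnia and headache are not among them; they are on the directed list.
- The history in 7.3 is limited to conditions that require treatment.
- Relatedness (8.1) needs only one criterion, such as a plausible mechanism, to be rated probable or definite. The ANOVA is on adverse event frequency, with no restriction to related events.
- The surveys are expressly not collected for safety (6.6), and the Insomnia Severity Index is scheduled only at baseline (6.9).

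Each is a partial filter; none is a rule.

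**Step 2: noise in the arm comparison under equal ascertainment.** Inputs: 110 per arm (330 enrolled, section 4.0, divided by 3); two-sided alpha 0.05. Assumed: new onset c = 8% on CBT and m = 22% on modafinil among those without the symptom; background b of 20% or 30%, always recorded.

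- Only new events counted: (1-b)c v (1-b)m.
- All counted: b + (1-b)c v b + (1-b)m.
- The difference is (1-b)(m-c) in both cases.
- Power = Φ[(d - 1.96·SE0)/SE1], where SE0 uses the pooled proportion and SE1 the separate ones.

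At b = 20%, d = 0.8 × 14 = 11.2 points. New events only: SE0 = 0.0438, SE1 = 0.0432, z = (0.112 - 0.0859)/0.0432 = 0.61. All events: SE0 = 0.0629, SE1 = 0.0624, z = (0.112 - 0.1233)/0.0624 = -0.18.

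| Background | Counted | CBT | Modafinil | Difference | Power |
|---|---|---|---|---|---|
| 20% | new only | 6.4% | 17.6% | 11.2 points | 73% |
| 20% | all | 26.4% | 37.6% | 11.2 points | 43% |
| 30% | new only | 5.6% | 15.4% | 9.8 points | 66% |
| 30% | all | 35.6% | 45.4% | 9.8 points | 31% |

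The risk difference does not change with the counting rule. The precision does.

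**Step 3: unequal review.** Within 12 weeks, section 6.9 gives CBT two post-baseline reviews (Weeks 8 and 12) and the modafinil arms four. Assume 40% background, each background symptom recorded with probability r per review, and new onset of 10% in both arms (no true difference). Recorded incidence is 1 - (1 - b[1-(1-r)^k])(1 - 0.10), with k = 2 or 4.

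- r = 50%: recorded background is 30.0% v 37.5%, and incidence is 37.0% v 43.8%, a false excess of 6.8 points on modafinil.
- r = 30%: the false excess is 9.0 points.
- r = 100%: it is zero.

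With 10% v 30% new onset (a true 20-point difference) and the same background, the recorded difference is 22.9, 19.3, 15.0 and 12.0 points at r = 30%, 50%, 70% and 100%. The apparent effect can be larger or smaller than the truth.

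**Step 4: the sleep subgroup.** Assume persisting insomnia is reported by 40-60% of the subgroup and 10% of the rest, with the same 8% new onset in both. Recorded insomnia is 1 - (1-0.4)(0.92) = 45% to 1 - (1-0.6)(0.92) = 63%, against 1 - (1-0.1)(0.92) = 17%. The gap is 28 to 46 points with no difference in harm.

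**The case against.** The strongest reply is that the sentence in 7.5 describes how participants are questioned, not which answers are recorded. Asking broadly and then applying judgement is normal practice, and the plan does hold a baseline review, a filter for chronic MS symptoms, change wording for two items, a treated-condition history and relatedness grading. This stands in part: the documents do not say that baseline symptoms will be counted. They leave the rule unstated, and it would be wrong to say that nothing is filtered.

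A reader might infer that arm differences are necessarily diluted. The documents do not support that. The extra reviews in Groups 2 and 3 push the other way. CBT calls may or may not serve as adverse event contacts, since 6.6 assigns safety assessment to the coordinator but includes any other contact. If frequency means event counts, an equal background leaves the expected difference unchanged and only adds noise.

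A reader might also blame the missing rule for a fall in the risk difference from 14 points to about 10. Step 2 shows otherwise: that fall arises because fewer people are at risk of new onset, and it occurs under either counting rule.

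Finally, a reader might call every subgroup comparison circular. That fits sleep, where insomnia is both a defining feature and a directed event. It is weak for depression, which is queried as worsening, and does not fit EDSS or MS subtype.

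**Conclusion.** The point holds as a missing counting rule combined with a subgroup comparison that answers the wrong question. Under the assumed rates, counting persistent symptoms costs about 30 points of power at 20% background (73% to 43%) and 35 at 30% (66% to 31%). These figures assume a yes/no measure, full recording of background symptoms, equal ascertainment and no worsening among those already affected. With the unequal review schedule, the bias can run in either direction, so no net direction should be claimed. The circularity is confined mainly to sleep. The lack of an arm-by-subgroup contrast applies to every subgroup and does not depend on any assumed rate. The change should be made, but it does not bear on the primary fatigue analysis.

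**What to change.** In 7.5, complete the directed checklist at the baseline AE/SAE review already in the schedule, and flag each later event as new or worse since that review.

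In 9.2 (Aim 3):
- analyse only new or worsened events;
- base the arm comparison on review time points common to all arms, and report the two extra early modafinil reviews separately;
- replace the comparison among subgroups with the arm difference within each subgroup and an arm-by-subgroup term.

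The safety reviews themselves stay as scheduled. The cost is CRF and SAP wording, with no added visits or participants. The downsides are lower event counts, some early modafinil events left out of the main comparison (hence the separate report), and low power for the interaction, which is best presented as estimates with confidence intervals.
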